1.0 Study Summary

Study Title	Feasibility, acceptability, and preliminary efficacy of combined transcranial direct current stimulation and mindfulness for pain after total knee arthroplasty
Study Design	Pilot randomized controlled trial
Primary Objective	Assess feasibility/acceptability of the intervention
Secondary Objective(s)	Assess preliminary effectiveness on pain intensity and pain interference with activities
Research Intervention(s)/Investigational Agent(s)	Combined Mindfulness-based intervention (MBI) + transcranial direct current stimulation (tDCS) vs sham MBI+sham tDCS
IND/IDE #	
Study Population	Preoperative patients undergoing total knee replacement (TKR)
Sample Size	40
Study Duration for individual participants	1 month
Study Specific Abbreviations/Definitions	CSPS: chronic post-surgical pain MBI: mindfulness-based intervention tDCS: transcranial direct current stimulation EG: experimental group CG: control group

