Study title:

Feasibility, Acceptability, and Preliminary Efficacy of Combined Transcranial Direct Current Stimulation and Mindfulness for Pain After Total Knee Arthroplasty

NCT Number: NCT05673720

Statistical analysis plan

October 10th, 2025

Data analysis was performed with R (Vienna, Austria) version 4.1+. Baseline demographic information was summarized using descriptive statistics. The distribution of all variables was examined before any analysis, using appropriate statistical tests like Shapiro's test for normality checking. If the assumption of normality was not met, equivalent non-parametric approaches were employed. Comparison between groups on changes from baseline in clinical variables as well as effect size (Cohen's d) calculation were conducted using Wilcoxon rank-sum test for score changes with non-normal distribution, and t -test for score changes with normal distribution. Considering the numerous repeated measures and the possibility of imbalances between measures, we conducted an analysis using a generalized mixed effects model to evaluate changes in all outcome measures for both preoperative and postoperative outcomes. Mixed effects models capture more information by offering more flexibility in the presence of missing data and treat time as a continuous variable. Mixed effects models are used for longitudinal observations and are capable of automatically adjusting for baseline differences, accounting for potential confounders (e.g., anxiety) when needed.

For the preoperative period, the analysis looked at differences between preoperative baseline and after 5 sessions with three fixed effects: Condition (Control vs. Treatment), Time (First vs. Last Session) and their interaction Condition*Time to test whether the treatment group showed different patterns of change compared to the control group over time in the preoperative period. For the postoperative period, the analysis looked at differences 1) between Day 1 Post-op vs. Day 5 Post-op, and 2) between Day 1 Post-op vs. 1-month post-op. Our model included three fixed effects: Condition (Control vs. Treatment), Time (Day 1 vs. Day 5 or Day 1 vs. 1-month post-op), and their interaction (Condition*Time) to test whether the treatment group showed different patterns of change compared to the control group over time in the postoperative period.

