The significance levels (Type-I error probability) for testing the difference between treatment groups over time was 5% and a p-value less than 0.05 was considered statistically significant. However, this level might seem arbitrary in pilot studies and we considered that in this preliminary study, $p < 0.10$ is suggestive (i.e. a trend) of a significant effect that warrants further study. We did not use any Bonferroni corrections for these pair-wise comparisons since a pilot study is usually designed for hypothesis generation instead of hypothesis testing.

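### The SAP states no test of whether the arms differ in postoperative opioid use; its Day 1-referenced interaction cannot answer Hypothesis 1

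*SAP*

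**What the plan says.** **Protocol.** Section 2.2, Hypothesis 1, concerns the level of analgesic use after surgery. Section 4.2 makes opioid dose over 5 postoperative days the primary endpoint, whereas section 1.0 gives the primary objective as "Assess feasibility/acceptability of the intervention". Section 17.1 (Aim 1) reduces three days of consumption to one value per patient and compares the arms with a t-test or its rank-based counterpart, followed by a covariate-adjusted regression.

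**SAP.** It is written in the past tense and mentions neither opioids nor analgesics. It names two kinds of analysis:

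- Two-sample tests: "Comparison between groups on changes from baseline in clinical variables".
- A "generalized mixed effects model to evaluate changes in all outcome measures for both preoperative and postoperative outcomes". After surgery, "the analysis looked at differences 1) between Day 1 Post-op vs. Day 5 Post-op, and 2) between Day 1 Post-op vs. 1-month post-op". The fixed effects are Condition, Time and their interaction, included "to test whether the treatment group showed different patterns of change compared to the control group over time in the postoperative period".

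No link function is named. The SAP remarks that mixed models "treat time as a continuous variable". It also says that p<0.10 "is suggestive (i.e. a trend) of a significant effect that warrants further study".

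**The concern.** A hypothesis about level needs a contrast between arms in level. For opioid use the SAP states none, and the one test whose purpose it does state for the postoperative period measures a difference in recovery slope.

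The p-value matters even in a pilot, because the SAP uses p<0.10 to decide what deserves further study. For opioids, the stated test can miss a steady benefit, or can point against the active arm when the benefit is largest early. Protocol 3.0 says analgesic use matters most in the first 48-72 hours, so an early benefit that then shrinks is a plausible pattern, although the protocol does not predict it.

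**Working it through.** **Which SAP analysis could test Hypothesis 1?**

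- *Change from baseline.* Protocol 4.2 defines the endpoint as doses after surgery, and the schedule in 4.0 marks it only on postoperative Days 1-3 and Month 1. There is no pre-treatment value, so these tests do not apply.
- *Aim 1 two-sample test.* It is not in the SAP. The sentence "We did not use any Bonferroni corrections for these pair-wise comparisons" does not name an opioid comparison either.
- *Mixed model.* It covers all outcomes. Its reference time is Day 1, and the last session is at T-3 (Protocol 6.1). The Day 5 contrast also needs a value that the schedule does not mark, although the text of 4.2 and 6.2 says 5 days.

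**What the interaction estimates.** Let D1 and D5 be the arm differences (active minus sham) on the model's scale. Then Condition*Time = D5 − D1. If D5 = D1 it is zero. If a benefit shrinks (D1 < D5 ≤ 0) it is positive, that is, against the active arm. The Month 1 contrast has the same form.

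**Inputs.** 40 completers (Protocol 12.1) at 1:1 (6.1) gives 20 per arm and 38 df. Tests are two-sided (17.1). The documents give no effect size, SD, dose level or between-day correlation r, so those are assumed. There is no planned power figure to reproduce.

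**Formulas (normal data, unit SD, identity link, complete data).** Standardised effects enter a noncentral t with noncentrality effect × √(20/2):

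- Interaction: (d1 − d5)/√(2(1 − r)).
- Total over k days: Σd/√(k + k(k − 1)r).

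For a benefit fading 0.8, 0.7, 0.6, 0.5, 0.4 SD over Days 1-5 at r = 0.5, the interaction effect is 0.4/√1 = 0.40, against the active arm. The 3-day total effect is 2.1/√6 = 0.857, in its favour.

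| Scenario and test | r=0.3 | r=0.5 | r=0.7 |
|---|---|---|---|
| Fading: interaction against active, p<0.05 | 17.9% | 23.4% | 35.6% |
| Fading: interaction against active, p<0.10 | 27.6% | 34.4% | 48.4% |
| Fading: t-test, 3-day total | 84.0% | 75.2% | 67.4% |
| Fading: t-test, 5-day total | 79.6% | 66.5% | 56.4% |
| Constant 0.8 SD: interaction, p<0.05 (half each way) | 5% | 5% | 5% |
| Constant 0.8 SD: t-test, 3-day total | 92.2% | 85.5% | 78.7% |
| Constant 0.8 SD: t-test, 5-day total | 96.0% | 88.9% | 80.7% |
| Constant 0.5 SD: t-test, 3-day total | 56.0% | 47.1% | 40.6% |
| Constant 0.5 SD: t-test, 5-day total | 64.2% | 51.2% | 42.4% |

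With a constant benefit, the interaction rejects in 10% of trials at p<0.10, again only its false-positive rate.

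**Skewed doses.** These are 10,000 simulated trials per scenario with lognormal doses and sham daily medians of 30, 25, 20, 15 and 10 mg. Entries are for r = 0.3/0.5/0.7 at p<0.05.

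| Scenario and test | log SD 0.6 | log SD 0.8 |
|---|---|---|
| Ratio 0.6 every day: log-scale interaction, either way | 5.3/4.9/5.2% | 4.5/5.3/5.0% |
| Ratio 0.6 every day: raw-mg interaction, against active | 35.8/41.5/49.4% | 17.8/20.9/26.0% |
| Ratio 0.6 every day: Wilcoxon, 3-day total | 93.1/86.9/81.3% | 72.0/63.5/56.7% |
| Ratio fading 0.6 to 0.8: log-scale interaction, against active | 24.2/31.4/47.6% | 15.6/19.2/29.9% |
| Ratio fading 0.6 to 0.8: Wilcoxon, 3-day total | 85.0/77.1/70.4% | 60.6/52.2/45.8% |

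The raw-mg row arises because a constant ratio of 0.6 is a median difference of 12 mg on Day 1 (0.4 × 30) but 4 mg on Day 5 (0.4 × 10).

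**The scale matters.** Under a log link with sham means of 60 then 20 mg, a constant 10 mg benefit gives ln(10/20) − ln(50/60) = −0.51, which favours active. A constant ratio of 0.75 gives exactly 0.

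**The case against.** The strongest reply is that Condition is itself a fitted effect and is a comparison of level. That is true, so a level contrast could be taken from the model. But the SAP assigns Condition no test and no coding, and its meaning depends on both. For a constant 0.8 SD benefit its power is:

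- 69.3% with Day 1 as the reference;
- 86.4/81.2/76.2% (r = 0.3/0.5/0.7) with sum-to-zero coding;
- 53.8/57.6/61.9% with time entered as 1 and 5, where Condition extrapolates to day 0.

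The last coding is only a possibility, since the SAP's remark on continuous time is general and its contrasts are written as pairs of times. None of these reproduces the multi-day summary of Aim 1.

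Other points stand in part:

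- The SAP is short and names no individual outcome, so the Aim 1 test may have been run and simply not described. The finding is about what is stated.
- The magnitudes rest on assumed effects. A benefit that grows after Day 1 would be detected in the active arm's favour: from 0 to 0.8 SD, in about 55/69/89% of trials. The fault is that the answer depends on the time pattern, whereas Hypothesis 1 concerns the level.
- This is a pilot, and section 1.0 makes feasibility primary. That limits the weight of any efficacy p-value. It does not change what the interaction estimates, and Hypothesis 1 still needs a test.

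**Conclusion.** The concern holds and should be corrected. For opioid use, the primary endpoint under Protocol 4.2, the SAP states no comparison of postoperative level between arms, and the Day 1-referenced interaction does not test Hypothesis 1. The cancellation of a constant benefit, and the adverse sign of a fading one, follow from algebra on whichever scale the model uses. Only the sizes depend on assumptions. Under the normal scenarios with 0.8 SD on Day 1, the interaction rejects in 5% of trials when the benefit is constant, and is significant against the active arm in 17.9% to 35.6% when it fades to 0.4 SD. The 3-day total has 78.7% to 92.2% and 67.4% to 84.0% power respectively.

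The finding does not extend to Hypothesis 2. Pain and the other scales have a preoperative baseline, so the SAP's change-from-baseline tests compare the arms validly. The SAP omits only which postoperative times they use.

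**What to change.** 1. State and report the Aim 1 comparison of summarised postoperative opioid use between arms, with the adjusted regression of Protocol 17.1, as the test of Hypothesis 1. Use one window, reconciling 5 days (text of 4.2 and 6.2) with 3 days (schedule in 4.0, and 17.1). Label any departure from Aim 1 as a change from the protocol.
2. Keep Condition*Time from Day 1 as a description of recovery slope, stating the link and the coding of Time and Condition. Do not use it as the test of Hypothesis 1 or 2.
3. For pain and the other scales, state the postoperative times of the change-from-baseline comparison, reconciling the SAP's Day 1 and Day 5 with the Day 3 and Month 1 of Protocol 4.0 and 17.1. Restore the baseline adjustment planned in 17.1, which gains precision and is not a bias correction.
4. Reconcile sections 1.0 and 4.2 on what is primary.

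The cost is SAP wording and a re-analysis of data already collected, with no new patients or visits. The 5-day window is available only if doses were recorded through Day 5, as the text of 4.2 and 6.2 requires.
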